3.0 STUDY DESIGN

3.1 Study Design (Main Study)

Thirty patients will be enrolled to evaluate the impact of adding the CCR5 inhibitor, MVC, to a stable suppressive HIV regimen on the rate of CD4+ T-cell recovery and gene expression profiles. At baseline whole genome expression (38,000 genes) profiles and extended flow cytometry will be performed on purified CD4+/CD8+ T-cells in all subjects. In addition, pre-MVC phase 2 CD4+ T-cell recovery rate will be estimated for each subject from historic laboratory data obtained during the 12 months prior to the baseline visit. All subjects will receive treatment intensification with MVC dose-adjusted to their background HIV regimen for 24 weeks. Regular visits will occur on weeks 2, 4, 8, 12 and 24 to assess efficacy, safety and medication tolerance. Additional microarray and

extended flow cytometric analyses will be performed at weeks 4 and 24 of MVC therapy. After 24 weeks of MVC treatment intensification, MVC will be discontinued, the original antiretroviral regimen will be maintained and subjects will return for a 12 week follow-up visit to evaluate on-going CD4+ T-cell recovery, continued HIV RNA suppression and any potential adverse events.

3.2 Study Design (CSF Sub-Study)

This is a sub-study of the MVC treatment-intensification protocol (i.e., a “piggyback” protocol). The primary eligibility criteria will be enrollment into the MVC parent study, ability to give informed consent to lumbar puncture (LPs), and the absence of medications or conditions that would contraindicate lumbar puncture (e.g., coagulopathy). Pre-treatment LPs will be performed, followed by a LP at week 4 of MVC treatment intensification (i.e., “steady state”). All LPs will be performed within one hour of a parent protocol-dictated blood draw, reducing the need for separate visits or additional phlebotomy. For subjects willing to undergo more than one LP, an additional LP will be performed at week 24 of MVC treatment intensification. The primary study outcomes will be measurement of MVC concentrations and reductions in markers of immune activation levels in CSF at week 4.

The study will aim to obtain 3 LPs in as many subjects as possible with the goal being at least two LPs separated by at least 4 weeks in up to 17 participants. After informed consent is obtained, subjects will undergo a brief screening to ensure the absence of contraindications to LP. If eligible subjects choose to enroll, subsequent visits will occur at major visits of the parent protocol (baseline, week 4 and 24). Based on prior experience we conservatively estimate that approximately 60% of subjects in the parent protocol will be willing to consent to lumbar puncture an average of 2.5 LPs per consenting subject. In total, we estimate that this CSF sub-study will yield approximately 43 LPs from individuals taking MVC. Post-dose timing of the lumbar punctures will be limited by the parent protocols but we will strive to vary the post-dose lumbar puncture interval in order to have approximately equal representation from two intervals.

- Interval 1: 2 - 6 hours post dose
- Interval 2: 6 - 12 hours post dose

If successful, this variation across the dosing interval will improve the accuracy of population pharmacokinetic modeling.

3.3 PBMC isolation

Viable PBMCs will be collected at pre-entry, baseline (day 0), weeks 4 and 24.

3.4 Flow Cytometry for CD4 and CD8 T-cells

Measurements for CD4+/CD8+ subsets will be determined at screening, weeks 2, 4, 8, 12, 24 and 12 weeks post CCR5-intensification. In addition, extended phenotype characterization will be performed at baseline, pre-entry and weeks 4 and 24 to determine the proportion of CD4+ and CD8+ lymphocytes that are naive (CD45RA+), activated (CD38+/HLA-DR+) or, among CD4+ cells, regulatory (CD25+CD127-).

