6.1 Schedule of Events – Clinical Evaluations

	Screening	Pre-Entry	Entry	Maraviroc Therapy Intensification (24 weeks)					Post-Maraviroc Intensificatoin	Treatment Failure, Tox or Premature D/C
	Within 30 days of entry	> 48 hrs before entry	Day 0	Week 2	Week 4	Week 8	Week 12	Week 24	Week 36	
Informed Consent	X									
Medical/Medication History	X									
Documentation of HIV	X									
Clinical Assessment / AE			X	X	X	X	X	X	X	X
Documentation of within criteria HIV RNA and CD4 prior to screen labs	X									
Complete Physical Exam			X							X
Targeted Physical Exam							X	X	X	
Start and Dispense Drug			X		X		X			
Stop and Collect Drug								X		X
Concomitant Medications	X		X	X	X	X	X	X	X	X
Adherence Assessment	X		X	X	X	X	X	X	X	X

CCTG 590
Protocol version 1.0
August 13, 2008

Schedule of Events – Laboratory Evaluations

	Screening	Pre-Entry	Entry	Maraviroc Therapy Intensification (24 weeks)					Post-Maraviroc Intensification	Treatment Failure, Tox or Premature D/C
	Within 30 days of entry	> 48 hrs before entry	Day 0	Week 2 (± 1 wk)	Week 4 (± 1 wk)	Week 8 (± 2 wk)	Week 12 (± 2 wk)	Week 24 (± 2 wk)	Week 36 (± 2 wk)	
Hematology (local lab)	X		X	X	X	X	X	X	X	X
Prothrombin time (local lab) †	X									
Chemistry / LFT (local lab)	X				X		X	X	X	X
Pregnancy test (local lab)	X	And anytime when suspected								
CD4+/CD8+ (local lab)	X		X	X	X	X	X	X	X	X
§ CD4 ≤ 350; HIV RNA ≤ 50	X									
Plasma HIV-1 RNA PCR (local lab)	X		X		X			X	X	X
Plasma for MVC levels †			X		X			X		
Extended flow cytometry & PBMC collection (UCSD lab)		X	X		X			X		
Microarray - PBMCs collection (local processing in real-time)			X		X			X		
Lumbar puncture†			X		X			X		
Plasma for storage			X		X			X	X	
Serum for storage			X		X			X	X	
Ship ambient sample for extended flow in real-time		X	X		X			X		
Ship frozen all stored PBMCs, plasma and serum									X	
HIV Resistance & Tropism testing										X

§ If available within 30 days of screen then do not need to repeat laboratory test and can use value obtained within 90 days as screen value

† Only for subjects co-enrolled in the central nervous system sub-study

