6.2 Definitions for Schedule of Events – Timing of Evaluations

6.2.1 Evaluations Prior to Study Entry

Occur prior to the subject taking any study medications, treatments, or interventions.

Patient Registration

A patient identification number (PID) will be assigned to each patient screened for the study. PIDs will include a site code and three-digit extension. PIDs should not be reassigned even if the patient fails to enter the study. The PID must be included on every CRF and patient blood sample. Each site must maintain a master list of PIDs in a central location. The patient registration and inclusion/exclusion must be entered on-line at www.cfar.ucsd.edu/intranet

Screening Site Clinical Labs

If plasma HIV-1 RNA and CD4+ T-cell counts were obtained at a CLIA-approved lab no more than 30 days prior to screening and results are available then these labs do not need to be repeated. Otherwise, a plasma HIV-1 RNA level and a CD4 cell count measurement need to be done at screening. Please record actual dates laboratories were done in the CRF.

All other study screening laboratories must be determined within 30 days of study entry (Day 0). Screening and entry evaluations must be separated by at least 48 hours. Hematology, chemistry and pregnancy testing will be coordinated through the site's local laboratory and results will be tracked by the CCTG Data Center.

Once the screening laboratories have been done the patient will be evaluated for study eligibility if all other entry criteria are satisfied.

The total blood volume for screening labs is 20 mL.

If the HIV RNA or other laboratory values are outside the eligible range, the site may re-screen a patient on one occasion. However, the study will not pay for additional re-screening laboratories.

Pre-Entry

Specimens for extended flow cytometry and PBMC storage need to be shipped by each site in real-time to the central laboratory (UCSD).

The total blood volume for pre-entry labs is 20 mL.

Entry

The entry evaluation should be scheduled within 30 days of the screening visit. Plasma and serum for storage should be obtained, however, specimens will be stored then shipped in batch on week 36 (end of study) along with other plasma, PBMC and serum specimens. The first dose of study medication should be given and witnessed by the study coordinator **after** drawing the entry laboratories.

The total blood volume for entry labs is 73 mL.

Lumbar puncture – 25 mL cerebral spinal fluid

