6.3.8 Immunologic Studies

Nadir CD4+

The subject's prior nadir CD4+ cell count (absolute value and date) should be documented during screening and, when possible, a copy of the nadir CD4+ cell count report should be included in the source document. If this documentation is not available, then subject recollection will suffice. For subjects who do not know the exact nadir value and for whom there is no source documentation, then recall of the categorical nadir (e.g., <50 , <100 , <200 cells/mm³) will suffice.

CD4/CD8

A screening CD4/CD8 count and percentage must be performed at the site's local laboratory within 30 days prior to study entry unless a CD4 value is available from a CLIA-certified laboratory within 30 days of screening.

Because of the diurnal variation in CD4+ and CD8+ cell counts; all determinations should be obtained consistently in either the morning or the afternoon throughout the study, if possible.

Blood volume: 5 mL

Extended Flow Cytometry Markers

Extended flow markers for activation, maturation and regulatory function will be evaluated on CD4+/CD8+ T-cells. Samples will be collected at pre-entry, entry and on weeks 4 and 24. Pre-entry and entry laboratories must be separated by a minimum of 48 hours. These analyses will be done on fresh samples in real-time. **Specimens will need to be shipped ambient, overnight and in real-time to the UCSD central laboratory.**

Blood volume: 10 mL

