9.2.2 Secondary

1. CD4+ T-cell absolute count and percentage at baseline, weeks 4 and 24.
2. The proportion of CD4+/CD8+ T-cell immune activation, maturation, regulatory and apoptosis markers at baseline and weeks 4 and 24.
3. Grades ≥ 2 laboratory abnormalities and signs and symptoms.
4. Paired plasma to CSF ratios of MVC concentration at week 4.
5. Soluble immune activation markers in CSF at baseline and week 4.
6. HIV RNA loads in CSF at baseline and week 4.

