9.4.3.1. Analysis of Secondary Objectives

Secondary analyses will include descriptive statistics and tests of significance between pre- and post-MVC intensification. All significance tests will be two-sided and no adjustment for multiple comparisons will be made. If necessary due to assumption failures, appropriate non-parametric statistical tests will be applied.

1. Differences in the change in CD4+ T-cell absolute count and percentage from baseline to week 4 and baseline to week 24 will be compared descriptively via separate paired Student t-tests. Repeated CD4+ T-cell absolute count measured at different time points (3 historic time-points, baseline, week 4, and week 24) will be treated as the outcome variable in a linear mixed-effects model. The primary fixed effects will include time, period (MVC vs. pre-MVC), and interaction between time and period; random effects will include both intercept and slope allowing each subject to have individual starting CD4+ T-cell counts and rate of change. Baseline covariate adjustment will be included if necessary. A significant interaction term between time and period with positive coefficient will indicate if the rate of CD4 recovery is greater during MVC compared to pre-MVC.

2. Differences in the rate of CD4+ T-cell recovery (absolute count and percentage) during MVC intensification in subjects receiving a PI/r- vs. NNRTI-based regimen will be compared via the linear mixed effects model. The fixed effects will include time, regimen (PI/r vs NNRTI), and regimen-by-time interaction; random effects will include both intercept and slope. The regimen-by-time interaction term in the model will indicate the difference in CD4+ T cell recovery rates between the two regimen groups. Baseline covariate adjustment will be included if necessary.

3. Differences in gene expression profiles between subjects receiving a PI/r vs. NNRTI-based regimen at baseline and weeks 4 and 24 will be examined by comparing the gene lists generated in the primary analysis by regimen type. If necessary, statistical modeling will include a dichotomous variable to indicate regimen type.

4. Differences in the proportion of CD4+/CD8+ T-cell immune activation, maturation, regulatory and apoptosis markers between baseline and weeks 4 and 24 will be compared cross-sectionally via McNemar's test or paired t-tests as appropriate.

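### Extended flow is measured twice before treatment, but no endpoint or analysis gives the pre-entry value a role; averaging it with entry would sharpen the secondary flow analyses at no sampling cost

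*Combined protocol and SAP*

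**What the plan says.** Section 3.4 schedules two flow samples before treatment: "extended phenotype characterization will be performed at baseline, pre-entry and weeks 4 and 24". Section 6.3.8 agrees ("Samples will be collected at pre-entry, entry and on weeks 4 and 24") and adds a spacing rule: "Pre-entry and entry laboratories must be separated by a minimum of 48 hours". It also says the assays are run on fresh samples in real time. In the laboratory schedule under section 6.1, the extended-flow row is marked at pre-entry, entry and weeks 4 and 24. It lacks the dagger that restricts an item to the CSF sub-study, so it applies to all 30 subjects.

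Section 3.3, on PBMC collection, shows how the protocol uses the word baseline: "Viable PBMCs will be collected at pre-entry, baseline (day 0), weeks 4 and 24". Pre-entry and day 0 are separate time points there.

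The flow endpoint in 9.2.2 is "The proportion of CD4+/CD8+ T-cell immune activation, maturation, regulatory and apoptosis markers at baseline and weeks 4 and 24". Item 4 of 9.4.3.1 follows it: "immune activation, maturation, regulatory and apoptosis markers between baseline and weeks 4 and 24 will be compared cross-sectionally", by McNemar's test or paired t-tests as appropriate. Item 5 is a Pearson correlation between early change in immune subsets and phase 2 CD4 recovery, and it does not say which pre-treatment value the change is measured from.

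**The concern.** Single-draw noise at baseline (assay error plus day-to-day fluctuation) enters every change score used for objective 1.2.2 and attenuates the correlations in item 5. A second untreated measurement that would reduce that noise is already drawn, shipped and assayed, yet the analysis section gives it nothing to do.

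Two further things are at stake. With two untreated values and no rule, someone must later choose between entry, pre-entry and their mean, in analyses that carry no multiplicity adjustment. And in a single-arm study, the pre-entry/entry pair is the only planned pre-treatment repeat of these markers. It shows how large ordinary short-term fluctuation is, which helps a reader judge a week 4 shift, although it does not replace a control arm.

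**Working it through.** **Inputs.** From the documents: n = 30 (section 3.1); two pre-treatment flow draws at least 48 hours apart (3.4, 6.1, 6.3.8); paired comparisons with weeks 4 and 24, two-sided (9.4.3.1). The documents give no SD, effect size, test-retest correlation or power for any flow marker, so there is no stated figure to reproduce. Assumed: equal variance at all visits, and alpha 0.05 for the power column.

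**Variance of a change score.** Let w be the noise variance of one draw and r·w the true between-subject variance of change.
- Entry alone: w + w + r·w = (2 + r)w
- Mean of pre-entry and entry: w + w/2 + r·w = (1.5 + r)w
- Proportional reduction: 0.5/(2 + r)

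**Link to correlations.** Let rs be the correlation between pre-entry and entry, and rl the correlation of either with an on-treatment sample. With unit variance, w = 1 − rs. The single-baseline change variance is 2(1 − rl), so r = 2(rs − rl)/(1 − rs). Short-term variation that the two close draws share, but the on-treatment draw does not, therefore counts towards r.

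**Results.** Power is for a paired t-test with n = 30, by the noncentral t, for an effect that has 80% power on entry alone.

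| Example rs, rl | r | Variance reduction | SE reduction | Equivalent n | Power |
|---|---|---|---|---|---|
| 0.7, 0.7 | 0 | 0.5/2 = 25% | 1 − √0.75 = 13.4% | 30/0.75 = 40 | 90% |
| 0.8, 0.7 | 1 | 0.5/3 = 17% | 8.7% | 36 | 87% |
| 0.9, 0.7 | 4 | 0.5/6 = 8% | 4.3% | 32.7 | 83% |
| 0.9, 0.5 | 8 | 0.5/10 = 5% | 2.5% | 31.6 | 82% |
| 1, 0.7 | no finite r | 0% | 0% | 30 | 80% |

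At r = 0 the change detectable with 80% power falls from 0.529 to 0.458 SD of the single-baseline change. A simulation of 1,000,000 draws agreed: variance 0.600 against 0.451 for correlations 0.7 and 0.7, and 0.602 against 0.552 for 0.9 and 0.7.

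**Item 5.** If the noise in the flow change is independent of CD4 recovery, the observed correlation is multiplied by √((2 + r)/(1.5 + r)). This is √(3/2.5) = 1.095 at r = 1, √(6/5.5) = 1.044 at r = 4 and √(10/9.5) = 1.026 at r = 8. At r = 0 there is no true variation in change to correlate, so the 25% ceiling cannot be claimed together with a gain for item 5.

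**Coverage.** Item 4 includes apoptosis markers. Section 3.4 lists naive, activated and regulatory cells, and section 6.3.8 lists activation, maturation and regulatory function. Neither names apoptosis, so the documents do not show that a pre-entry apoptosis value will exist. The variance formula also does not apply directly to a dichotomised marker under McNemar's test.

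**The case against.** The strongest reply is that nothing is wrong: a single day 0 baseline is valid and unbiased, the study is a pilot powered for gene expression, and these are secondary analyses. All of that stands, and the point is one of efficiency.

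A reader might infer that the plan excludes the pre-entry value. It does not. The omission is by silence, and a minimum gap between two pre-treatment draws is compatible with an intended duplicate baseline. But section 3.3 equates baseline with day 0, and no section says the values are combined. If that was the intention, it still has to be written down.

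A reader might also take 25%, or 40 subjects in place of 30, as the expected gain. The documents do not support that. It requires no true variation between subjects in their change, whereas hypotheses 1c and 1d (2.3.1) suppose that changes in activation and naive cells track CD4 recovery. Draws as little as 48 hours apart may also share short-term variation, which shrinks the gain further. On the other side, 48 hours is a minimum, so the actual gap may be longer.

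**Conclusion.** The point holds as a free improvement of low severity. Under equal variances, averaging cannot lose precision, and it gains some unless the two pre-treatment draws are perfectly correlated. The reduction in change-score variance lies between 0% and 25%. Where it falls depends on correlations the documents do not report, so confidence is high in the direction and not in the size.

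The benefit is confined to the secondary flow analyses (items 4 and 5), for markers actually measured at both visits. It would be wrong to infer any effect on the primary endpoint: microarray samples are collected only at entry and weeks 4 and 24, so there is no pre-entry expression value to average.

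**What to change.** In 9.4.3.1, items 4 and 5, add wording to this effect:
- For each flow marker measured at both visits and analysed as a continuous proportion, baseline is the mean of the pre-entry and entry values, or the single available value if one is missing.
- If a marker is dichotomised for McNemar's test, the cut-off is applied to that mean.
- Agreement between pre-entry and entry is reported as an estimate of assay plus short-term variability.

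Align the wording of the flow endpoint in 9.2.2 with this definition, and state whether apoptosis markers are part of the pre-entry panel.

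The cost is a few sentences in the analysis section. No extra draw, shipment, assay or visit is needed, and clinical management does not change.

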1.2 Secondary Objectives

- 1.2.1 To compare the rates of phase 2 CD4+ T-cell recovery prior to and during 24 weeks of MVC therapy intensification.
- 1.2.2 To evaluate the impact of MVC therapy intensification on persistent immune activation and maturation phenotype (as measured by flow cytometry) during viral suppression.
- 1.2.3 To characterize differences in the gene expression profiles associated with MVC therapy intensification in individuals receiving a PI/r- vs. NNRTI-based regimen.
- 1.2.4 To evaluate the safety and tolerability of adding MVC to a stable antiretroviral regimen as assessed by the rate of > grade 2 adverse clinical or laboratory events.
- 1.2.5 To characterize cerebral spinal fluid concentrations of MVC compared to plasma concentrations.
- 1.2.6 To evaluate the impact of MVC therapy intensification on persistent immune activation (as measured by soluble and cellular markers) in the central nervous system.

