2.3.1. Hypotheses

1. We hypothesize that expression will decrease among genes involved in immune activation (NF-kB, MAPK, nuclear factor of activated T-cells, MYD88 and STAT1), apoptosis (Fas ligand and TRAIL) and

trafficking/repopulation of T-cells (CCR5, MIP-1 α , MIP-1 β and RANTES) and increase among genes involved in tissue repair (platelet-derived growth factor, insulin-like growth proteins and osteoblast-specific transcription factor).

- a. The gene expression profiles induced by MVC will be associated with a favorable increase in the rate of CD4+ T-cell recovery.
- b. The rate of CD4 recovery (cells/month) will be greater during MVC compared to before.
- c. The proportion of cells expressing activation/ apoptosis markers will decrease from baseline and this decrease will be associated with improved CD4 recovery.
- d. The proportion of naïve cells will increase from baseline and this increase will be associated with improved CD4 recovery.
- e. The rate of CD4 recovery will be greater among those subjects receiving PI-containing treatment regimens compared to those receiving NNRTI-containing treatment regimen.

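### Naive T-cells are gated on CD45RA alone, so a change in CD45RA+ effector cells during maraviroc would be read as a change in naive cells, mainly in the CD8+ lineage (low severity)

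*Combined protocol and SAP*

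**What the plan says.** Section 3.4 sets out the extended phenotyping. Its purpose is "to determine the proportion of CD4+ and CD8+ lymphocytes that are" in one of three classes: "naive (CD45RA+), activated (CD38+/HLA-DR+) or, among CD4+ cells, regulatory (CD25+CD127" (the quotation stops just before the closing minus sign and bracket). Activated and regulatory cells each have a two-marker definition; naive cells have one marker, applied to both lineages.

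No other section adds to this. Objective 1.2.2 refers to "persistent immune activation and maturation phenotype (as measured by flow cytometry"). Section 6.3.8 says "Extended flow markers for activation, maturation and regulatory function will be evaluated on CD4+/CD8+ T-cells", on fresh samples at pre-entry, entry and weeks 4 and 24, and names no antibody. Section 9.2.2 item 2 lists "The proportion of CD4+/CD8+ T-cell immune activation, maturation, regulatory and apoptosis markers at baseline and weeks 4 and 24".

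Two hypotheses in section 2.3.1 use these subsets. Hypothesis 1c reads "The proportion of cells expressing activation/ apoptosis markers will decrease from baseline and this decrease will be associated with improved CD4 recovery". Hypothesis 1d reads "The proportion of naïve cells will increase from baseline and this increase will be associated with improved CD4 recovery", without saying whether CD4+ or CD8+ naive cells are meant. In section 9.4.3.1, item 4 compares the marker proportions before and during treatment by McNemar's or paired t-tests, and item 5 correlates early subset change with CD4 recovery (Pearson). On error control, "All significance tests will be two-sided and no adjustment for multiple comparisons will be made"; no alpha level is given for these tests.

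**The concern.** CD45RA is not specific to naive cells. Antigen-experienced, terminally differentiated effector T-cells re-express it, mostly in the CD8+ lineage. This is general immunology; the documents do not mention it. Followed as written, the gate counts naive cells and CD45RA+ effectors together, while hypothesis 1d concerns naive cells only.

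The endpoint would mislead if effectors move during the 24 weeks. A fall would hide a true naive rise. A rise would be reported as naive recovery that had not occurred. The naive subset matters to the study's reasoning: section 2.1 describes second-phase recovery as new T-cells from the thymus and peripheral expansion, and section 2.3 plans a mechanistic model that draws partly on CD4/CD8 subset changes. A mislabelled subset would feed into that model.

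**Working it through.** The plan gives no effect size, SD or power for this endpoint, so there is no figure to reproduce. The power table in section 9.3 concerns gene expression.

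**Inputs from the documents.** Naive = CD45RA+ (3.4); 30 patients, single arm, within-patient comparison (3.1); two-sided unadjusted tests (9.4.3.1).

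**Assumed inputs.** Alpha 0.05; SD of the within-patient change 5 or 8 percentage points, the same for either gate; all subset frequencies and changes below.

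**Step 1: what is measured.** Let N be the percentage of truly naive cells and E the percentage of CD45RA+ effectors. The gate records N + E, so

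measured change = ΔN + ΔE.

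**Step 2: constant effectors.** If ΔE = 0, the measured change is ΔN. For example, 20 + 20 = 40 becomes 24 + 20 = 44: a 4-point naive rise is recorded as 4 points. A paired t-test on absolute differences is unaffected.

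**Step 3: moving effectors.** 20 + 20 = 40 and 24 + 16 = 40: a 4-point naive rise beside a 4-point effector fall is recorded as zero.

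**Step 4: consequence for the paired test.** Two-sided paired t-test, n = 30, 29 degrees of freedom, noncentrality = (measured change / SD) × √30. True naive rise 3 points:

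| ΔE (points) | Measured change | Chance of a significant rise, SD 5 / SD 8 | Chance of a significant fall, SD 5 / SD 8 |
|---|---|---|---|
| 0 | +3 | 88.8% / 51.0% | 0.0% / 0.0% |
| −1 | +2 | 56.3% / 26.2% | 0.0% / 0.1% |
| −2 | +1 | 18.4% / 9.7% | 0.1% / 0.4% |
| −3 | 0 | 2.5% / 2.5% | 2.5% / 2.5% |
| −5 | −2 | 0.0% / 0.1% | 56.3% / 26.2% |

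The first row also describes the opposite error. With ΔN = 0 and ΔE = +3 the measured change is again +3, so a naive rise that did not occur would be declared with probability 88.8% or 51.0%.

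**Step 5: how large an effector fall cancels a 3-point naive rise.** Relative fall needed = 3 / E:

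| N | E | Effector share of the gate, E/(N+E) | Relative fall needed |
|---|---|---|---|
| 40 | 2 | 2/42 = 4.8% | 3/2 = 150%: impossible |
| 40 | 5 | 5/45 = 11.1% | 3/5 = 60% |
| 25 | 15 | 15/40 = 37.5% | 3/15 = 20% |
| 20 | 25 | 25/45 = 55.6% | 3/25 = 12% |

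Cancellation is implausible where effectors are few and easy where they are many. If CD45RA+ effectors are mainly CD8+, the problem lies mainly there.

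**Step 6: the correlation.** With S the CD4 recovery rate, cov(ΔN + ΔE, S) = cov(ΔN, S) + cov(ΔE, S). If ΔE is the same in every patient, the correlation is unchanged. If ΔE varies between patients, it adds noise, and if it is itself related to S, the coefficient no longer describes naive cells alone.

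**The case against.** Several points on the other side stand.

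- **Proportional dilution.** A reader might infer that the effector share of the gate shrinks the observed effect in proportion. That is true only of a relative change. Items 4 and 5 work on changes in the proportions, and a constant effector percentage drops out (step 2).
- **A predicted offset or reversal.** A reader might infer that the protocol's own model implies a falling effector share. It does not. Hypothesis 1c concerns activation and apoptosis markers, and activation is defined by CD38+/HLA-DR+. Nothing links that population to CD45RA+ effectors or predicts their direction. Reversal needs effectors to fall by more points than naive cells rise, and no figure in the documents supports it.
- **CD4+ cells.** If hypothesis 1d means CD4+ naive cells, the distortion is probably small, as the first row of step 5 illustrates.
- **Incomplete list.** Section 3.4 may not be the full panel. Apoptosis markers appear in hypothesis 1c, section 9.2.2 and section 9.4.3.1 but not in 3.4, so the laboratory may already run a second maturation marker.
- **Stakes.** Section 9.1 calls this a pilot powered for gene expression, and PBMCs are stored at the same visits (6.3.12), which may allow some later phenotyping.

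These points limit the size and severity but do not remove the defect. The plan states a rule for naive cells, applies it to CD8+ as well as CD4+ cells, and leaves 1d open as to lineage. Followed as written, that rule does not isolate the population the hypothesis names. Stored cells are not a planned remedy: section 6.3.8 specifies fresh samples.

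**Conclusion.** The point holds as a construct-validity defect in one part of one secondary endpoint, mainly for CD8+ cells. The CD45RA+ proportion tests hypothesis 1d only if CD45RA+ effectors do not shift during treatment (paired comparison) and do not vary in their change between patients (correlation). Masking, reversal and a false naive rise are possibilities under assumed subset changes, not findings from the documents. The size cannot be derived from the plan: the power figures rest on assumed SDs, alpha and subset changes, and the premise about CD45RA rests on general immunology. Severity is low. The primary gene-expression analysis, the CD4 slope analysis and the activated and regulatory subsets are untouched.

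**What to change.** In sections 3.4, 6.3.8 and 9.2.2 item 2, define naive cells by CD45RA together with a second differentiation marker, for example CCR7, CD62L or CD27, on the same fresh sample at pre-entry, entry and weeks 4 and 24. Use that population in section 9.4.3.1 items 4 and 5, report CD4+ and CD8+ results separately, and state in hypothesis 1d which lineage is meant. Settle the gate before the first pre-entry sample so that all visits share one definition.

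If the panel cannot be changed, name the endpoint the CD45RA+ proportion and do not interpret it as naive for CD8+ cells.

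The cost is one more antibody and re-compensation of the panel, assuming the instrument has a free channel; the documents do not describe its configuration. No extra blood draw or visit should be needed, because the sample is already taken. If the laboratory already runs a second marker, or if the endpoint is only renamed, the change is wording alone.
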